## 7.5 6 weeks post-op

All patient participants will be reviewed in a routine outpatient clinic at 6 weeks postoperatively (from date of surgery). Please also see section 7.12 on contingency planning.

PROMS questionnaires to be completed are listed below. The Oxford Hip Score is to be completed first, others are shown in a recommended order of completion of most recent recall period:

- Oxford Hip Score
- EQ-5D-5L™
- Self-Administered Patient Satisfaction scale
- Forgotten Joint Score
- Work Productivity and Activity Impairment—Specific Health Problem

Data will also be collected Adverse Events of Special Interest; these will primarily be surgical complications, such as but not limited to returns to theatre for dislocation, fracture or wound problems; any prescriptions for antibiotics will be noted and any unanticipated contact with the surgical team or GP regarding the surgery.

The earliest this visit can occur is 3 weeks postop and the latest is 12 weeks postop from the date of surgery. Visits outside of these parameters will be recorded as protocol deviations but will not affect the patients continuing participation in the trial.

Every effort should be made to meet the patient in person during the visit. Should this not be possible the questionnaires should be posted as soon as possible to the patient for their completion. Details on how and when to return the questionnaires are included within the covering letter. (See also section 7.7 Loss to follow-up.)

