## 11.2.2 Secondary

- 1. Adherence to the protocol will be measured by:
  - i. the number of minor (e.g. visit time-point violation) or major (e.g. violation of inclusion criteria) protocol deviations collected on a patient participant and site level. (The definitions of minor and major protocol deviations will be in accordance with LCTC categorisations that will be allocated to each deviation by the CI after assessment of the details)
  - ii. the percentage of patients in each arm that were accidentally unblinded
- 2. Trial withdrawal rate at 6 weeks and 3-6 months will be measured using the total number of patients randomised in the study. In addition, withdrawal rates will be presented by trial withdrawal reasons and withdrawal stage for both arms.
- 3. Patient participant population characteristics will be measured by collecting the following information:
  - i. Age
  - ii. BMI
  - iii. Proportion of missing data
  - iv. Loss to follow up
- 4. Clinical and patient reported data will be measured by collecting the following information:
  - i. Patient participant-reported outcomes including change in OHS, FJS, WPAI-SHP, SAPS score and quality of life measured using the EQ-5D-5L™ at 6 weeks and 3-6 months
  - ii. Revision rate, defined as the number of patient participants needing Revision arthroplasty within 3-6 months of surgery
  - iii. Infection rate, measured as the rate of re-operation for infection within 3-6 months of surgery
  - iv. Length of stay, measured in hours
  - v. Operation time, measured in minutes

**IRAS Ref: 271885** Page 50 of 89

- vi. Incidence of treatment cross over during surgery
- vii. Incidence of intra-operative surgical complications, the proportion of patient participants experiencing greater than grade III severity will be measured and reported according to Clavien Dindo classification system^24.
- viii. Incidence of postoperative surgical complications, the proportion of patient participants experiencing greater than grade III severity will be measured and reported according to Clavien Dindo classification system^24.
- 5. Completeness of the EQ-5D-5L™ and Healthcare Resource Use Survey will be measured by using the follow methods:
  - i. Descriptive statistics will be used to assess the frequency of missing data for the EQ-5D-5L™ and Healthcare Resource Use Survey.
  - ii. Any patterns in missing data will be identified through the use of descriptive statistics

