#### The following are reportable to LCTC:

- Any Adverse Event of Special Interest (AESI) with a severity grading of 3 or above according to the Clavien Dindo classification system^24 (see table D).
- Any Adverse Device Event that meets the definition of serious (see section 12.5) and is assessed as being related a device (i.e. an implant or bone cement).

No other safety events are required to be reported to LCTC. All safety events (regardless of the requirement to report to LCTC) are to also be recorded and reported as per local policy.

**IRAS Ref: 271885** Page 54 of 89

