## 12.4 Assessment of Severity

Important Note: A distinction is drawn between **severe** and **serious**. Severity is a measure of intensity, whereas seriousness is defined using the criteria in Section 12.5. However, any AE's with a severity grading of 4 or 5, according to the Clavien Dindo classification system^24 (i.e. life-threatening or fatal), also meet the criteria of serious.

Table D: Clavien Dindo classification system^24.

Grade	Definition
1	
 
Any deviation from the normal postoperative course without the need for pharmacological treatment or surgical, endoscopic and radiological interventions.
 
Allowed therapeutic regimens are: drugs as antiemetics, antipyretics, analgetics, diuretics and electrolytes and physiotherapy.
 
This grade also includes wound infections opened at the bedside.
 

2	
 
Requiring pharmacological treatment with drugs other than such allowed for grade 1 complications.
 
Blood transfusions and total parental nutrition are also included.
 

3a	Requiring surgical, endoscopic or radiological intervention – not under general anaesthesia.
3b	Requiring surgical, endoscopic or radiological intervention – under general anaesthesia.
4a	
 
Life-threatening complication (including CNS complications*) requiring intermediate care or intensive care management – single- organ dysfunction (including dialysis).
 

4b	
 
Life-threatening complication (including CNS complications*) requiring intermediate care or intensive care management – multi- organ dysfunction.
 

5	Death of a patient.
*brain ha	aemorrhage, ischemic stroke, subarachnoidal bleeding, but excluding

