## 12.8.1 Adverse Events of Special Interest

Any AESI with a severity grade of 3 or higher is to be recorded on the Adverse Events CRF.

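### Complication outcomes 4(vii) and 4(viii) count only Clavien Dindo grades above III, while the protocol collects adverse events of special interest from grade 3 upwards

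*Protocol*

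**What the plan says.** Two complication outcomes are defined in Protocol section 11.2.2. Item 4(vii) is "Incidence of intra-operative surgical complications, the proportion of patient participants experiencing greater than grade III severity", and item 4(viii) is "Incidence of postoperative surgical complications, the proportion of patient participants experiencing greater than grade III severity". Both are graded on the Clavien Dindo scale.

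The collection rules use a different cut:

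- Section 12.3 makes an AESI reportable to the trials centre "with a severity grading of 3 or above according to the Clavien Dindo classification system".
- Section 12.7.1 sets the same floor for entering AESIs in the patient's notes.
- Section 12.8.1 says: "Any AESI with a severity grade of 3 or higher is to be recorded on the Adverse Events CRF".

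Table D in section 12.4 defines grade 3a as "Requiring surgical, endoscopic or radiological intervention – not under general anaesthesia" and grade 3b as "Requiring surgical, endoscopic or radiological intervention – under general anaesthesia". Grades 4a and 4b are life-threatening complications with organ dysfunction, and grade 5 is death.

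Section 7.5 describes the AESI data sought at six weeks as mainly surgical complications and gives as examples "returns to theatre for dislocation, fracture or wound problems".

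Section 11.2.2 also lists revision arthroplasty, item 4(ii), and re-operation for infection, item 4(iii). Neither carries a grade threshold.

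**The concern.** The outcome and the data behind it are cut at different points on the same scale. A return to theatre without organ dysfunction or death is a grade 3 event under Table D. It meets the recording threshold but fails the counting threshold. These are the kind of events that section 7.5 gives as examples.

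Intra-operative and post-operative safety is secondary objective 5 (section 2.3), and items 4(vii) and 4(viii) are its general complication measures. If the outcomes are computed as written, their proportions omit the grade 3 events that the trial has gathered. The protocol fixes the threshold itself, in two places. An analysis plan that follows it repeats the gap, and one that uses grade III or above departs from the protocol.

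**Working it through.** The protocol states no figure that depends on this threshold, so there is none to reproduce. The check compares definitions, followed by an illustration of size.

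**Step 1. Apply both thresholds to Table D (section 12.4).** The grades are 1, 2, 3a, 3b, 4a, 4b and 5.

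| Rule | Where | Grades included |
|---|---|---|
| Greater than grade III | 11.2.2, items 4(vii) and 4(viii) | 4a, 4b, 5 |
| Grade 3 or above | 12.3, 12.7.1, 12.8.1 | 3a, 3b, 4a, 4b, 5 |
| Collected but not counted | difference | 3a, 3b |

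**Step 2. See whether another outcome in 11.2.2 counts the grade 3 events.**

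| Grade 3 event | Counted under |
|---|---|
| Revision arthroplasty | 4(ii) |
| Re-operation for infection | 4(iii) |
| Return to theatre for dislocation, without revision | none |
| Fracture fixation without revision | none |
| Haematoma evacuation, not for infection | none |

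Dislocation, fracture and haematoma are all listed AESIs in Table C, so the last three rows reach the Adverse Events CRF and then enter no defined outcome.

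**Step 3. Size.** Let p be the share of patients whose worst complication is grade 3. The protocol gives no such rate, so p is assumed. With n = 40 (section 4.1), the expected number left out of 4(vii) and 4(viii) is 40p, and the chance of at least one is 1 − (1 − p)^40, taking patients as independent.

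| Assumed p | Expected of 40 | Chance of at least one |
|---|---|---|
| 1% | 0.4 | 33% |
| 2% | 0.8 | 55% |
| 3% | 1.2 | 70% |
| 5% | 2.0 | 87% |

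These counts include grade 3 revisions and infection re-operations, which step 2 shows are picked up elsewhere. They are therefore upper limits, at each assumed rate, for events that enter no outcome at all. One omitted patient moves the overall proportion by 1/40 = 2.5 percentage points.

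**Step 4. Chance that the outcome as written is empty.** At an assumed grade 4–5 risk of 0.5%, (1 − 0.005)^40 = 0.82. At 1%, (1 − 0.01)^40 = 0.67. The chance of at least one counted patient is then 18% to 33%.

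**The case against.** The best defence is that this is a slip for grade III or above, in two descriptive items of a 40-patient feasibility study whose primary outcome is recruitment. No grade 3 AESI data are lost: the events are on the CRF, and section 7.6 asks again about returns to theatre. The steering committee oversees complications (section 18.3). The full trial is to be planned from recruitment, PROM variance, retention and the intraclass correlation, not from complication rates. Even the corrected proportion would be imprecise: 2 events in 40 has an exact 95% interval of about 0.6% to 17%. All of this stands, and it sets the weight of the point. It does not make the two thresholds agree.

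A reader might infer more than the protocol supports:

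- **That re-operations as a class vanish from the outcomes.** They do not. Items 4(ii) and 4(iii) count revision and re-operation for infection at any grade, and a re-operation with organ dysfunction or death still counts in 4(vii) or 4(viii).
- **That the outcome is almost bound to read zero.** Under the rates assumed in step 4, zero is likely (67% to 82%) but not near-certain, and the rates are not the protocol's.
- **That the grade 3 recording floor contradicts the six-week data collection in section 7.5.** That section says antibiotic prescriptions and unplanned contacts are noted. Section 12.8.1 governs only the Adverse Events CRF, and section 12.3 gives reasons for the limited safety reporting.
- **That the scale cannot be used intra-operatively.** In Table D only grade 1 is framed by the postoperative course ("Any deviation from the normal postoperative course without the need for pharmacological treatment"); grades 2 to 5 are not.

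**Conclusion.** The mismatch is real, and it follows from the protocol's wording alone. As written, 4(vii) and 4(viii) exclude grades 3a and 3b, although AESIs of those grades are reported and recorded. Grade 3 interventions that are neither a revision nor a re-operation for infection enter no defined outcome, so the complication proportions for secondary objective 5 are understated.

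The size depends on rates that the protocol does not give. At assumed grade 3 rates of 1% to 5%, about 0.4 to 2.0 of 40 patients would be left out of the two items, some of them counted under 4(ii) or 4(iii). The data needed to put this right are already collected. This is a minor consistency correction to a descriptive secondary outcome and does not affect recruitment, the stop/go criteria or the PROM estimates.

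**What to change.** In section 11.2.2, change the threshold in items 4(vii) and 4(viii) to grade III or above, so that it matches sections 12.3, 12.7.1 and 12.8.1. Make the change before the final analysis and carry it into the analysis plan and table shells.

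The cost is a few words in two items. No new data collection, CRF change or wider AESI recording is needed, because grade 3 AESIs are already on the Adverse Events CRF.

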## 11.3 Sample Size

As this is a feasibility study, no formal sample size calculation based on observing a clinically relevant difference will be obtained. A sample size target of 40 patients (with at least 2 surgeons having 6 or more patients) will enable us to estimate of variance at a surgeon and patient level variability to facilitate sample size calculation of a future study.

Based on current recruitment information we propose a recruitment period of up to 6 months. Using three recruiting sites (yielding 40 recruited patient participants by 6 months) this corresponds to a recruitment rate of 2.22 patient participants per site per month considering that sites will be opened within the first two months.

In order to better inform sample size calculations for the future study, the standard error along with 95% confidence intervals of the variance estimate for change at 6 weeks and 3-6 months of the retention rate and each of the PROMs investigated (OHS, FJS, SAPS and WPAI-SHP), along with the visual analogue scale from EQ-5D-5L™ is going to be reported from a single longitudinal model of all data. In addition, Inter class correlation (ICC) within hospitals for the PROM data will also be estimated which will also inform the sample size calculation for the future full study.

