## 7.11 Quality of Life and Health Economics

Health Related Quality of Life and Health Economics outcomes measures

Health-related quality-of-life (HRQL) and other outcomes for use in the health
economics component of the study will be assessed using the following
questionnaires:

- Oxford Hip Score (OHS)
- EuroQol 5 Dimension, 5 Level Quality of Life Questionnaire (EQ-5D-5L™)
- Self-administered Patient Satisfaction scale (SAPS)
- Forgotten Joint Score (FJS)
- Work Productivity and Activity Impairment-Specific Health Problem (WPAI-SHP)
- Healthcare Resource Use Survey

Baseline data will be collected prior to the patient participant being randomised, with further collections at 6 weeks and 3-6 months post-operation. The only exclusions to this are the Health Resource Use Survey data, which is only collected at baseline and 3-6 months post-operation and SAPS data, which is not collected at baseline and will only be collected at 6 weeks and 3-6 months post-operation.

- The Oxford Hip Score© is used to assess joint-specific pain and functional limitations encountered by the patient participant in day-to-day activities over the preceding 4 weeks.
- EQ-5D-5L™ is a preference-based HRQL measure comprising five domains, each with five levels. HRQL scores can be attached to each of the possible 3125 health states it describes.
- Self-administered Patient Satisfaction scale is a tool to measure patient satisfaction with their operation, pain, and ability to do daily activities and recreational activities.
- The Forgotten Joint Score is a 12 question scale used to measure joint awareness. It has been extensively validated to assess outcomes after total hip arthroplasty.
- Work Productivity and Activity Impairment-Specific Health Problem records data on work time and productivity over the preceding 7 days.
- The Healthcare Resource Use Survey is a HipHOP specific questionnaire

**IRAS Ref: 271885** Page 44 of 89

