## 11.5 Analysis Plan

Feasibility and overall recruitment rate will be assessed at the opened sites by calculating the total number of patient participants randomised per month and the ratio of successful recruitment to eligible patients approached. Furthermore, observed recruitment rates, by site and overall, will be summarised along with a 95% confidence interval.

**IRAS Ref: 271885** Page 51 of 89

Much of the analysis will be performed using summary statistics and graphics. No formal assessments of efficacy, cost or safety across treatment arms will be made. All presentations of the data will take the form of summary analysis and graphical representations. Continuous data shall be presented using measure of median (interquartile ranges), whereas categorical data shall be presented in terms of frequencies of counts and associated percentages.

Primary and secondary outcomes will be compared between the two arms using a chisquared or Fisher's exact test.

All analyses shall be carried out on an intention to treat basis, retaining all patient participants in their initially randomised groups irrespective of any protocol deviations. The exception to this is the analysis of safety data which shall be analysed on the safety set which is defined by the type of arthroplasty that patients receive.

Feasibility of the study will be measured on the ability of the study to meet the recruitment targets and Stop/go criteria are defined on this basis.

Following 6 months of active recruitment, a target of 40 patient participants is set. If recruitment is  $\geq$  80% of this target ( $\geq$ 32 patients) a future full study can be considered feasible. If the observed recruitment rate is between 50% and 80% of the target (20-31 patients) then a future full study could potentially go ahead only if satisfactory measures can be taken to improve recruitment. Such measures must be realistic and have support of the study sponsor. If recruitment is less than 50% of the anticipated rate ( $\leq$ 19 patients) than the study won't be considered feasible to evolve into a full one in the future.

In addition, in order for the study to be considered feasible, it should not demonstrate any serious issues related to randomisation process, patient participant retention and/or protocol deviations.

Statistical analyses will be performed using a suitable recognised statistical software such as Stata v15 or above, R v3.3.0 or above and SAS v9.3 or above.

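### Section 11.3 promises planning quantities the design cannot give (change in SAPS, a change variance for retention) and overstates how well surgeon and hospital variance can be estimated

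*Protocol*

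**What the plan says.** Protocol section 11.3 states that "no formal sample size calculation based on observing a clinically relevant difference will be obtained". It rests the target of 40 on variance estimation instead: "A sample size target of 40 patients (with at least 2 surgeons having 6 or more patients) will enable us to estimate of variance" at surgeon and patient level, for use in sizing a later trial. To inform that calculation it will give the standard error and "95% confidence intervals of the variance estimate for change at 6 weeks and 3-6 months of the retention rate and each of the PROMs". The list that follows is OHS, FJS, SAPS and WPAI-SHP, with the EQ-5D-5L visual analogue scale added, all from one longitudinal model. A within-hospital ICC is also to be estimated and used for planning. Section 4.1 sets three sites.

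Section 11.2.2, item 4(i), lists as an outcome at 6 weeks and 3-6 months "Patient participant-reported outcomes including change in OHS, FJS, WPAI-SHP, SAPS score and quality of life". Section 7.11 describes "SAPS data, which is not collected at baseline and will only be collected at 6 weeks and 3-6 months post-operation". The baseline list in section 7.2 omits SAPS, and Table B in section 7.8 marks it only at the two post-operative visits.

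Section 2.2 says that the full trial's primary outcome will be a patient-reported functional score, and that its sample size needs the standard deviation and the rate of loss to follow-up. Section 2.3 makes these planning statistics a secondary objective. No section says whether the full trial will analyse final scores, change scores or baseline-adjusted scores.

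**The concern.** Section 11.3 is where the protocol says what this study will hand to the full trial. Two of the promised items do not exist as described. Two others, surgeon variance and hospital ICC, can be computed but would be too imprecise to plan with, although the text says that the design will enable the first and that the second will inform planning. For the remaining questionnaires the text names only the variance of change, which is the right input for one of the three usual analyses.

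At stake is whether the full trial's sample size is built on the right inputs. Taken literally, 11.3 could lead a later team to use a change variance for an analysis that is not of change, or to take a cluster variance from two or three clusters at face value.

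**Working it through.** **The plan's own figure.** The only derived number in 11.3 is the recruitment rate: 40 / (3 sites x 6 months) = 2.22 per site per month. It reproduces. The target of 40 has no formula.

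**SAPS.** Sections 11.2.2 and 11.3 ask for change at 6 weeks and at 3-6 months. Sections 7.2, 7.8 and 7.11 give no baseline. The only computable difference is 3-6 months minus 6 weeks, which is one quantity and not a change at each visit.

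**Retention.** Each patient gives one yes/no result per visit. The natural summary is a proportion with a confidence interval. There is no within-patient change in a score, so a model of questionnaire scores yields no change variance for it.

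**Precision of a variance.** A variance s² on d degrees of freedom has 95% limits d·s²/χ²(0.975, d) and d·s²/χ²(0.025, d). As multiples of the estimate:

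| Component | df | Lower | Upper |
|---|---|---|---|
| Surgeons, at the floor of 2 | 1 | 0.20 | 1,018 |
| Hospitals, 3 | 2 | 0.27 | 39.5 |
| Patients, 40 | 39 | 0.67 | 1.65 |

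The first two rows are a best case, because they treat the cluster means as known without patient-level error. On the SD scale the patient row is √0.67 = 0.82 to √1.65 = 1.28, that is -18% to +28%. With 32 patients, the lower edge of the top recruitment band in section 11.5 (31 df), it is 0.80 to 1.33.

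**Hospital ICC.** Take 3 sites of m = 13 and an observed ICC of 0.05 (assumed). Then F = (1 + 12 x 0.05) / (1 - 0.05) = 1.684 on 2 and 36 df.
- Upper limit: F_U = 1.684 x 39.47 = 66.5, and (66.5 - 1) / (66.5 + 12) = 0.83.
- Lower limit: negative, so set to 0.

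If the true ICC is 0.05 (assumed), the between-hospital component is estimated at or below zero in about 44% of trials; at 0.02 it is 54%.

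**Surgeon ICC.** By the same method, two surgeons of 6 at an observed 0.05 give 0 to 0.995. Six surgeons of about 7 still give 0 to 0.53.

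**Change variance against the alternatives.** Assume equal SDs at baseline and follow-up, with correlation r between them (not in the protocol).
- Change: 2(1 - r)·SD²
- Final score: SD²
- Baseline-adjusted: (1 - r²)·SD²
- Change / baseline-adjusted = 2/(1 + r)
- Change / final score = 2(1 - r)

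| r | Change / adjusted | Change / final | Total N: change, final, adjusted |
|---|---|---|---|
| 0.3 | 1.54 | 1.40 | 654, 468, 426 |
| 0.5 | 1.33 | 1.00 | 468, 468, 352 |
| 0.7 | 1.18 | 0.60 | 282, 468, 240 |

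The totals are illustrative, for an assumed difference of 0.3 SD at 90% power and two-sided 5%. For example, the final-score N is 2 x (1.960 + 1.282)² / 0.3² = 233.5, so 234 per arm and 468 in total.

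**The case against.** Much can be said for the plan.

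- **Full-trial analysis.** It is not fixed, so a reader who infers that change variance would mis-size the full trial goes further than the documents allow. It is correct for a change-score analysis. A longitudinal model can also yield per-visit variances and the baseline correlation, and section 11.5 announces a separate analysis plan that could list them. This stands, and the point is conditional.
- **Summaries as medians.** Section 11.5 says "Continuous data shall be presented using measure of median (interquartile ranges", and a reader might conclude that no SD will be available. It will: 11.3 promises a model variance, and its square root is an SD.
- **Two surgeons is a floor.** More may contribute, so the 1-df figure is the worst case. This stands, although six surgeons still leave the ICC interval at 0 to 0.53. Both components can be calculated; the fault is precision.
- **Design effect.** A reader might infer that an ill-estimated ICC would inflate the full trial by 1 + (m - 1)·ICC and that an external clustering allowance is needed. The documents do not support this. Section 11.1 randomises individuals 1:1 within site, so between-site variance largely cancels from the treatment contrast and the factor is about 1 - ICC. Inflation would need treatment effects that differ by site or surgeon, which the protocol does not discuss.
- **Small consequences.** Section 11.2.2 already reports withdrawal and loss to follow-up, so the retention wording does little harm. SAPS measures satisfaction while the full trial's primary outcome is to be functional. The numerical progression criteria rest on recruitment. All of this is fair, and it limits the seriousness without making the text right.

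**Conclusion.** Two statements are wrong as written and need no assumption to show it: change in SAPS at the two post-operative visits, and a change variance for retention.

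A third overstates precision. Three hospitals give limits of 0.27 to 39.5 times the estimated variance and an ICC interval of about 0 to 0.83 (at an observed 0.05, 13 per site). The two-surgeon floor gives 0.20 to about 1,018 times. These components can be described but should not feed a calculation as point values. Patient-level variance, by contrast, is usable at 40 patients.

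The fourth is conditional. Naming only the change variance could mis-size the full trial. Under a baseline-adjusted analysis it would oversize by 1.54 to 1.18 for r from 0.3 to 0.7. Under a final-score analysis it would oversize below r = 0.5, match at 0.5 and undersize above. Both r and the analysis method are assumptions. The correction is worth making because these inputs are a stated objective, but it does not touch the study's main recruitment question.

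**What to change.** - **SAPS:** delete change for it in 11.2.2 item 4(i) and in 11.3, and report the score at each post-operative visit.
- **Retention:** report a proportion with an exact 95% confidence interval at each visit, outside the longitudinal model.
- **OHS, FJS, WPAI-SHP and the EQ-5D-5L visual analogue scale:** keep the change variance, and add the SD at each visit and the baseline-to-follow-up correlation, with confidence intervals. Whichever analysis the full trial adopts can then be sized.
- **Cluster components:** restate 11.3 so that patient-level variance is the planning quantity. Report surgeon and hospital components descriptively with their intervals, and do not use them as point inputs to the full trial's sample size.

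This takes protocol and analysis-plan wording and a few more model outputs, with no new data or patients. The downside is a less favourable statement of what the study can estimate.
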